Methods: The study conforms to the Consolidated Standards of Reporting Trials recommendations. Ethical approval will be sought from the University Health Network (UHN) Research Ethics Board. This proposed study is a single centered, factorial, randomized placebo-controlled trial with two independent variables, depth of capsaicin application and dose of capsaicin, for a total of four treatment arms and two control treatment groups.

Discussion: This will be the first study that assesses the B-mode ultrasound image texture of induced sensitized muscles, and will provide more evidence on muscle motor unit activity and regional changes of central sensitization. Findings from this study may support one of few hypotheses proposed delineating the involvement of central sensitization in the development of trigger points.

Trial Registration: Name: National Institutes of Health ClinicalTrials.gov.
Identifier: NCT03944889
Date of Registration: May 07 2019
URL: <https://clinicaltrials.gov/ct2/show/NCT03944889>

Keywords: myofascial pain syndrome; ultrasound; image texture; electromyography; central sensitization; trigger points

List of Abbreviations:

US: Ultrasound

EMG: Electromyography

MPS: Myofascial pain syndrome

MTrP: Myofascial trigger points

SEA: Spontaneous endplate activity

Background

Myofascial pain syndrome (MPS) is a prevalent chronic pain disorder primarily characterized by myofascial trigger points (MTrP). MTrP are stiff taut bands of muscle distinguished by hypersensitivity on palpation and local twitch responses on snapping palpation.[1] A current clinical challenge in chronic pain care, applicable to myofascial pain, is early detection and effective treatment targeting the underlying pathophysiology.

There is limited knowledge on the pathophysiology and mechanisms underlying MTrP and its development. Ultrasound studies have been able to characterize trigger points[32,45,46], however there are some contradictory findings on whether these areas are hyperechoic or hypoechoic[45,46]. More recently, texture feature analysis have been shown to differentiate between healthy and MPS as well as active and latent trigger points[32]. Trigger points are typically located within the region of the muscle belly, where there is a high distribution of motor endplates.[2,3] Seventy-one percent of acupoint locations in the body, which are regions associated with motor points, motor endplates, or major motor nerve pathways overlap with common MTrP.[4]

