- e. Is there a location dependent EMG response to capsaicin induced sensitization? In other words, do the texture features or EMG responses from muscles that lie anatomically distant from the location of the site of intramuscular capsaicin injection have changes from their baseline calculations? This would test the hypothesis that type III and IV afferents have an influence on the anterior horn cells that lie distant to the ones that are supplying muscle fibers in the vicinity of the stimulated sensory afferents.
- f. Is there a dose dependent EMG response of motor units to capsaicin induced sensitization? Here, the hypothesis of causality will be assessed in a preliminary manner. If there is a relationship then further experiments that more thoroughly assess causality will be needed.

Methods & Design

Study Design:

The study conforms to the Consolidated Standards of Reporting Trials recommendations.

Ethical approval is approved by the University Health Network (UHN) Research Ethics Board.

This study is registered under the National Institutes of Health ClinicalTrials.gov.

This proposed study is a single centered, factorial, randomized placebo-controlled trial with two independent variables, depth of capsaicin application and dose of capsaicin, for a total of nine treatment arms. The first between groups variable will be topical capsaicin application

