and injectable capsaicin injection. Within each partition there will be three treatments: control, 50 micrograms, 100 micrograms. One-hundred micrograms reported to be an effective high dose of capsaicin.[13] The control group will receive a topical skin lotion which is inert and has no sensitization effect. An equal number of participants will be allocated to each of the six treatment groups using an electronic randomization generator. Block randomization will be used to ensure equal allotment into each group. An alternate member of the research team will conduct the randomization schedule a priori. Participant allocation will be concealed by placing their assignment in an envelope and delivered to participants by the same member of the research team uninvolved in the measurement or randomization protocols. Participants and investigators will be blinded to the delivered dose; however, the type of capsaicin delivery cannot be blinded from either participants or investigators. The member of the research team conducting the randomization schedule and concealing allocation will have knowledge of and keep track of the doses contained in the containers and vials of the topical and injectable capsaicin, respectively. They will deliver the appropriate dose to the team member implementing the experimental protocol to ensure there is blinding with respect to dose. This individual will not be involved in participant recruitment.

Participants

Recruitment

Participants will be recruited from UHN and the University of Toronto clinics, employees, volunteers, visitors, students, and external participants. UHN is a tertiary healthcare centre with eight hospitals located in Toronto, Canada and the University of Toronto is an academic institution with a main campus located in close proximity to the main UHN hospitals

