perform a gradually decreasing contraction to rest. This will be performed four times for each type of study intervention and before as well as after each intervention, namely topical control cream, topical capsaicin at 50ug and 100 ug, injection of the superior aspect of the superior fascia followed by intramuscular injection with these two concentrations of capsaicin. The placement of these latter will be verified by ultrasound guidance. The intramuscular needle will then be removed and participants will be bandaged and cared for appropriately by the expert physician performing the experiment. Following this, ultrasound pictures will be taken again from the same muscles mentioned previously. Participants will be re-examined to determine if there were any adverse effects from the experimental procedures. If any occurred, then these will be carefully managed by the medical members of the research team and recorded. Participants will be asked to remain at the lab for an additional 30 minutes to ensure they are well prior to leaving (Figure 2).

Central sensitization and measurement techniques

Inducing central sensitization

Central sensitization will be induced using capsaicin according to the established technique.[13,24,25] It induces increased pain severity at high doses relative to heat and elicits a dose dependent pain responses, allowing for more easily quantifiable measurements.[26] Capsaicin delivery induces both primary and secondary nociception suggesting that central mechanisms are involved in the nociceptive response, also termed as central sensitization.[13,14] Previous evidence has confirmed that capsaicin can sensitize nociceptive and mechanoheat receptors outside of the region of primary hyperalgesia, with speculation that it can also sensitize chemonociceptive receptors.[13] Therefore, capsaicin can effectively be used to induce central sensitization.

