2. Safety evaluation The investigating physician monitors the patient clinically for signs of distress. The methods and timing for assessing, recording, and analyzing safety parameters. Any signs of distress noted by investigating physician will be assessed clinically and appropriately managed. The information will be recorded on the patient's data form. The study team will discuss all incidents and any potential causal link to the study interventions. Patients will be provided with a contact number for the principal

investigator in order to report any changes that occur during or after the study. Our publication will include a list of any adverse events or intercurrent illness encountered. Any patient who experiences an adverse event will be triaged to their family physician or local emergency department as necessary. They will be contacted after to obtain information on the course of their treatment and the outcome of the event.

3. Sample size calculation.

Using GPower V3.0.10 (Dusseldorf, Germany), considering a medium effect size (Hedge's G) of 0.5 and a moderate correlation coefficients (0.5) among repeated measures, sample size calculation determined that a minimum of 70 participants would be required to detect differences via repeated measures ANOVA (two measurement as before and after among 7 groups) with 80% power and an alpha of 0.05. We aim to recruit 84 participants to account for potential attrition (~20%) of participants given the study duration and frequency of follow-up visits.

We plan to recruit equal number of men and women. To date, there are no reported sex differences in induction of Central Sensitization using Capsaicin among males and females with neurological impairments.

4. Statistical analysis plan

Baseline participants' characteristics including demographics will be analyzed using appropriate descriptive statistics. Mean and standard deviation will be calculated for continuous variables. Categorical variables will be presented as numbers and percentages. To test the change in ultrasound images from baseline to experimental conditions, the

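### The sample size is computed for seven groups while the design text gives six or nine, and recruiting 84 leaves 67 after a 20% loss, below the plan's own minimum of 70

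*Combined protocol and SAP*

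**What the plan says.** The protocol gives several group counts.

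- Abstract, Methods: a factorial design "for a total of four treatment arms and two control treatment groups", which makes six.
- Study Design, opening sentence on the design: the same two factors, depth and dose, but "for a total of nine treatment arms".
- Study Design, next lines: two routes, and "Within each partition there will be three treatments: control, 50 micrograms, 100 micrograms". Then "An equal number of participants will be allocated to each of the six treatment groups".
- Experimental Protocol: no number, but a list of interventions, namely "topical control cream, topical capsaicin at 50ug and 100 ug", then "injection of the superior aspect of the superior fascia followed by intramuscular injection with these two concentrations of capsaicin".
- Inducing central sensitization: the topical control is the cream base, and the injection control is saline. Saline does not appear in the Experimental Protocol list.
- Sample size calculation (item 3): a "minimum of 70 participants would be required to detect differences via repeated measures ANOVA (two measurement as before and after among 7 groups"), with a Hedges' g of 0.5, a correlation of 0.5 between repeated measures, 80% power and alpha 0.05. The target is 84, to cover attrition of about 20%.

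The purpose statement at the end of the Background adds that capsaicin is given at three concentrations. Study Design names two capsaicin doses plus control.

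**The concern.** The number of groups enters a repeated measures ANOVA calculation directly, through the degrees of freedom and the number of participants per arm. A calculation for seven groups does not size a six-group or a nine-group trial. Block randomisation into equal groups also cannot be set up until the count is fixed: 84 participants give 14, 12 or 9.33 per arm.

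The attrition allowance looks wrong as well. Multiplying by 1.2 does not offset a 20% loss. If the loss is as large as the plan expects, the trial ends below the number that the plan calls its minimum.

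A lesser matter is that 70 cannot be checked from the stated inputs alone. Hedges' g compares two groups, an ANOVA with several groups needs Cohen's f, and the text does not say which effect (group, time or group by time) was sized.

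**Working it through.** **Inputs.** From the sample size section: k = 7 groups, m = 2 measurements, ρ = 0.5, alpha 0.05, power 80%, N = 70, target 84. Assumed, because the plan gives no f: f = 0.25, which is g/2 for two groups of equal size. The other group counts, 6 and 9, come from the Abstract and Study Design.

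**Formula.** The group-by-time effect has a noncentral F distribution with k − 1 and N − k degrees of freedom. Two conventions for the noncentrality are possible:

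- N-based: λ = f² × N × m/(1 − ρ)
- error-df: λ = f² × (N − k) × m/(1 − ρ)

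**Reproducing 70.** With k = 7 and f = 0.25, m/(1 − ρ) = 2/0.5 = 4 and f² × 4 = 0.25.

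- N-based: the smallest N with 80% power is 62 (63 in equal groups).
- Error-df: λ = 0.25 × (68 − 7) = 15.25 at N = 68, power 80.5%. The minimum is 68, or 70 in equal groups, where power is 82.1%. This matches the plan.

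Entering 0.5 directly as f with λ = f²(N − k) and no correlation term gives the same answer, since 0.5² = 0.25. Entering 0.5 as f with the correlation term gives 21 (N-based) or 26 (error-df). So 70 is attainable, but only through choices that the text does not state.

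**Attrition.**

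- 84/70 = 1.2.
- 84 × 0.8 = 67.2, so 67 completers, three below 70.
- 1 − 70/84 = 16.7%, the largest loss that still leaves 70.
- 70/0.8 = 87.5, so 88 would be the target that keeps 70 after a 20% loss.

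**Effect of the group count** (group by time, f = 0.25, ρ = 0.5, losses spread evenly):

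| Groups | Minimum N, N-based (equal groups) | Minimum N, error-df (equal groups) | Power at 67, N-based | Power at 67, error-df | 84 per group |
|---|---|---|---|---|---|
| 6 | 58 (60) | 63 (66) | 87.4% | 83.7% | 14 |
| 7 | 62 (63) | 68 (70) | 84.6% | 79.7% | 12 |
| 9 | 69 (72) | 77 (81) | 79.0% | 71.7% | 9.33 |

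The loss that 84 can absorb, measured against the equal-group minimum, follows as 1 − minimum/84. For six groups it is 28.6% (N-based) or 21.4% (error-df), for seven 25.0% or 16.7%, and for nine 14.3% or 3.6%.

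**Where seven might come from.** The Experimental Protocol list can be counted in two ways. If fascial and intramuscular injection are separate arms, one control cream plus three sites × two doses makes seven, but this leaves out the saline control. If the two injections are given one after the other in the same participant, the list has three topical arms and two injection arms, and adding saline makes six, in line with the Abstract. Nine would follow from three sites × three levels. These are inferences; the text confirms none of them.

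**The case against.** Four points can be made for the plan.

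First, 70 is not an arithmetic error. It is reproduced for the effect that the analysis most plausibly targets. The statistical analysis plan regresses the after-minus-before difference in EMG amplitude on intervention group, which with two measurements is the group-by-time effect. This stands, and it reduces the matter of unstated inputs to a reporting gap.

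Second, the attrition figure is given as approximate, the shortfall is three participants, and the trial calls itself exploratory. This also stands as to size. With seven groups, power at 67 is still about 80–85%. It does not make 84 a target that allows for a 20% loss from 70.

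Third, the flow chart (Figure 1) is not available here and may list the arms. Even so, no figure can make six, seven and nine agree in the text.

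Fourth, the Experimental Protocol list may be the source of the seven. That is possible, but the same list also supports six, and the count of seven drops a control that another section specifies.

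A reader might infer that the trial is underpowered, for instance by taking 0.5 to be a capsaicin-versus-control difference in standard deviations. The documents do not support this. They do not say what the 0.5 measures, and turning f into such a difference requires an assumed pattern of arm means, for example equal means at both doses, which the research question on dose dependence leaves open.

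A reader might also infer that losses would fall mainly on controls, since participants who are not sensitised are withdrawn and Study Design says "The control group will receive a topical skin lotion which is inert and has no sensitization effect". The withdrawal rule is worded around capsaicin application, and its application to controls is unclear. That is a separate design question and no part of this arithmetic.

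**Conclusion.** The point holds. The sample size is calculated for a group count that the stated design does not give, and the recruitment target does not preserve the plan's minimum at the attrition it assumes. The shortfall is three participants. Its consequence depends on the arm count: at 67 completers the stated 80% is met for six groups, is borderline to adequate for seven, and is missed for nine under both conventions. These results rest on f = 0.25 for group by time, ρ = 0.5 and evenly spread losses; only the correlation is in the plan. The review does not claim that 70 is wrong, that power fails, or that any particular arm list or dose is the intended one.

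**What to change.** 1. Reconcile the Abstract, the purpose statement in the Background, Study Design, Experimental Protocol, Inducing central sensitization and the sample size section, together with Figure 1, to one arm list. It should say whether fascial and intramuscular injection are separate arms or sequential in one participant, and whether saline is an arm.
2. Re-run the calculation for that number of groups. Name the effect (group by time), the f entered and the noncentrality option, and replace Hedges' g by that f.
3. Only after the re-run, keep recruitment at 84 and state one of two things: the loss that 84 covers relative to the new minimum (16.7% if the minimum remains 70), or the power with 67 completers. If nine arms are confirmed, say that power at 67 is about 72–79% at f = 0.25 and that 84 cannot be divided equally among them.

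Handle the withdrawal of participants who are not sensitised as a separate item.

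The cost is one re-run, a rewritten sample size paragraph and consistent arm wording across the sections named. Recruitment stays at 84.

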in Toronto. Advertisements, flyers, and in person recruitment will be employed to collect the necessary sample size for the study. The recruitment procedures will run in line with the approved guidelines from the UHN research ethics boards. Participants will not be coerced into participating and will be informed that they have the right to withdraw at any time during the experimental procedures. They will also be informed they have the right to withdraw their data prior to publication. Participants will be briefed and consented on recruitment prior to commencing the study procedures. Participant treatment allocation will be recorded on a separate document until all of the data collection is complete and the data is analyzed.

Eligibility Criteria

Female or male participants who meet the following inclusion criteria will be included in the study: (1) participants are healthy with no past medical history (2) a visual analogue score below 3 indicating low pain severity, however, ideally who complain of no pain (3) right or left handed, (4) normal body mass index, (5) have sufficient command of the English language to provide informed consent and to understand the study protocols, (6) participants agree to sign a consent to volunteer for the research.

Exclusion Criteria

Participants who meet one or more of the following criteria will be excluded: (1) history of pain, (2) physical examination detection of myofascial trigger points, (3) participants present with a history of pain related disturbances such as poor sleep, cognitive disturbances, psychiatric disorders, (4) history of general medical disorder that may affect the outcome of the study such as diabetes mellitus, (5) and a history of cervical radiculopathies or (6) history of inflammatory arthropathy.

Experimental Protocol

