texture features will be computed in MATLAB and principal component analysis will be computed to reduce the variables. A repeated measures MANOVA will be applied for each intervention group. To test the change in EMG within and between groups a repeated measurement ANOVA will be applied considering each intervention group as a factor. The dependent variable would be considered as pain intensity, duration, and area of pain in separate analysis. Data distributions would be first checked with the Shapiro-Wilk to conform the normal distribution of the data. Additionally, we will test for the homogeneity of variance using Mauchly's test as well as correcting the degrees of freedom if necessary [40]. If the assumption of normality not met, for all skewed data an appropriate transformation will be used. We will construct univariate and multivariable linear regression models of differences in EMG amplitude (differences between after and before) as a function of intervention groups when adjusted for important covariates. Due to small sample size in each group, there is not possible to adjust for several covariates. Therefore, in a univariate model we will find the most important ones. For initial selection of relevant variables, all variables with a p-value ≤ 0.2 in the univariate analysis will be selected and retained in the multivariable analysis.

All Statistical analyses will be conducted with SAS for Windows (version 9.3; SAS Institute, Inc, Cary, NC). Using a two-sided test a P-value ≤ 0.05 will be considered as statistically significant.

Discussion

This will be the first study that assesses the effect of capsaicin induced central sensitization on ultrasound texture features and muscle motor unit activity. Findings from this

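### The only evidence offered on sex concerns people this trial does not enrol, and no stated step secures the planned 1:1 sex ratio within arms

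*Combined protocol and SAP*

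**What the plan says.** The sample size section (item 3 under Secondary outcomes) states "We plan to recruit equal number of men and women" and then, without a reference, that "there are no reported sex differences in induction of Central Sensitization using Capsaicin among males and females with neurological impairments". Nothing else in the document deals with sex, apart from the eligibility criteria admitting both sexes.

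Inclusion criterion 1 (Eligibility Criteria) requires that "participants are healthy with no past medical history". The exclusions add a "history of general medical disorder that may affect the outcome of the study such as diabetes mellitus" and "a history of cervical radiculopathies".

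Study Design says "An equal number of participants will be allocated to each of the six treatment groups using an electronic randomization generator" and "Block randomization will be used to ensure equal allotment into each group". It names no stratification factor and no block size.

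In the Statistical analysis plan (item 4), the texture MANOVA and the EMG repeated measures ANOVA name only intervention group. Covariates appear only in the linear regression of EMG amplitude change. There the plan says small groups rule out adjusting for several of them, and "all variables with a p-value ≤ 0.2 in the univariate analysis will be selected and retained in the multivariable analysis". Sex is not named.

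**The concern.** There are two linked gaps.

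First, the reassurance does not transfer. It describes people with neurological impairments, whereas this trial takes healthy volunteers. It also concerns whether capsaicin induces sensitisation equally in men and women. The primary outcomes are changes in image texture and in motor unit recruitment and amplitude, and the sentence does not address them.

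Second, the equal recruitment target is not carried into the arms. Every planned inference is within or between intervention groups, so an overall 1:1 ratio does not by itself protect a comparison of groups of 12 to 14 people. If men and women respond differently to capsaicin, an arm's mean change depends partly on its sex mix. The analysis offers no dependable correction: neither the texture nor the EMG group analysis has a sex term, and the regression includes sex only if a screen happens to select it.

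**Working it through.** **Population.** The sentence on sex: people with neurological impairments; induction of sensitisation; no citation. The trial: healthy people with no past medical history; texture, recruitment and amplitude as primary outcomes. The sentence matches the trial on neither population nor outcome.

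**Inputs for balance.** The target of 84 is from the sample size section (70 × 1.2 = 84). Equal recruitment by sex gives 42 men and 42 women. Study Design allocates equally to six groups (84/6 = 14 each), while the sample size text uses seven (84/7 = 12 each), so both are shown. The plan gives no figure for sex balance to reproduce. Its minimum of 70 can be recovered (68, rounded up to seven equal arms, taking 0.5 as a repeated-measures f in the SPSS convention), but nothing below depends on that. Assumption: without stratification, sex is independent of position in the allocation list.

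**One arm.** The number of men in an arm of 14 is hypergeometric (84, 42, 14).
- P(exactly 7:7) = 0.23.
- P(4:10 or worse in either direction) = 0.14.
- P(at least one of six arms is that unbalanced) = 0.56.
- With seven arms of 12, P(at least one arm is 2:1 or worse) = 0.93.

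**Two arms.** SD of the difference in proportion male = √[(2/n) × 0.25 × 84/83].
- n = 14: √(0.1429 × 0.25 × 1.012) = 0.19.
- n = 12: √(0.1667 × 0.25 × 1.012) = 0.21.

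**Shift in a contrast** = difference in proportion male × sex effect on the change score. The documents give no sex effect; 0.3 to 0.5 SD is an assumption.
- Typical (one SD, n = 14): 0.19 × 0.3 = 0.06; 0.19 × 0.5 = 0.10 SD.
- Tail (10:4 against 4:10, a gap of 6/14 = 0.43): 0.43 × 0.3 = 0.13; 0.43 × 0.5 = 0.21 SD.

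**How often the tail occurs (six arms of 14).** For two specified arms, P(gap ≥ 6 men) = Σ C(14,a)·C(14,b)·C(56,42−a−b)/C(84,42) over |a−b| ≥ 6, which is 0.037 (0.036 by simulation). For some pair among the six arms, exact enumeration gives 0.30 (0.29 by simulation).

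**Scale.** With 14 per arm, the standard error of a two-arm difference in change is √(2/14) = 0.38 SD. The typical shift is therefore 0.15 to 0.25 of a standard error (0.057/0.38; 0.095/0.38). The tail shift is about 0.34 to 0.57.

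**Does the screen recover sex?** Take 35 men and 35 women (the minimum of 70) and a two-sided t test at 0.2 with 68 degrees of freedom, critical value 1.29. The noncentrality is d × √(35/2).
- d = 0.3: noncentrality 1.25, P(selected) = 0.49.
- d = 0.5: noncentrality 2.09, P(selected) = 0.79.

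This route exists only for EMG amplitude. Texture has none.

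**The case against.** The strongest reply is that randomisation balances sex in expectation and the standard error already allows for chance imbalance. Stratifying by sex is thus a precision option in a self-described exploratory trial, not a condition of validity. That stands, and it limits the point to efficiency.

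Several stronger readings are tempting, and the documents do not support them:
- A reader might infer that sex differences in muscle size or subcutaneous tissue feed into the dose and route contrasts. The planned analyses are of before/after change, so stable additive differences between men and women cancel. Only a sex difference in response carries over, and the documents give no evidence of one.
- A reader might take 0.56 as the chance of the 0.13 to 0.21 SD shift. It is the chance that at least one arm is 4:10 or worse. A gap of six or more men between two specified arms has probability of about 0.04.
- A reader might say that the plan dismisses sex. It sets a deliberate 1:1 recruitment target and leaves the covariate screen open to sex.
- A reader might say that the arms will not be balanced, or that stratification is ruled out. The text is silent on stratification, so balance is not ensured, which is a weaker statement.
- A reader might say that neurological impairment is a listed exclusion. It is not; the mismatch follows from inclusion criterion 1.

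What survives is the mismatched sentence, the absence of a stated balancing step, and the absence of a sex term in the main texture and EMG analyses.

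**Conclusion.** The point holds as a modest one. The sentence on sex is uncited and describes a population and an endpoint that are not this trial's, so it should not stand as support. No stated step carries the equal recruitment into the arms, and the analysis would pick up a sex effect only in the EMG-amplitude regression, and there unreliably.

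The cost is lost precision through chance imbalance: typically 0.06 to 0.10 SD on a two-arm contrast against a planned effect of 0.5, and 0.13 to 0.21 SD at a 10:4 versus 4:10 split. These sizes rest on 42 men and 42 women, six arms of 14, unstratified allocation and an assumed sex effect on change of 0.3 to 0.5 SD. If sex does not affect the response, the shift is zero. With seven arms of 12 the typical shift is about the same (0.21 × 0.3 = 0.06; 0.21 × 0.5 = 0.10). The case for acting is that the remedy costs almost nothing.

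**What to change.** 1. Randomisation: generate separate permuted-block lists for men and women from the existing electronic generator, and name sex as the stratification factor in Study Design.
2. Analysis: include sex as a prespecified fixed term in the texture and EMG group comparisons and in the EMG-amplitude regression, outside the p ≤ 0.2 screen.
3. Text: delete the sentence about neurological impairments, or replace it with cited evidence from healthy people that bears on the outcomes measured.

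At randomisation, completed blocks with 42 of each sex give 7+7 per arm with six arms or 6+6 with seven. The number of arms must be reconciled first: the abstract gives four plus two, Study Design gives both nine and six, and the sample size text gives seven. Attrition and the withdrawal of participants who are not sensitised can still unbalance the analysed groups. The fixed sex term deals with that.

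Cost: a second randomisation list and one model degree of freedom per analysis. No extra participants, visits or measurements are needed.
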